
Termination Criteria

Participants may be terminated for any of the following: (a) participant request to exit or withdraw consent; (b) development of risk of harm to self or others that requires immediate intervention; (c) alcohol, drug, medication use that would interfere with dronabinol or has level 1 evidence for severe drug-drug interaction with dronabinol; (d) development of a systemic, medical, neurologic, or psychiatric illness requiring treatment that would exclude participation; (e) clinical deterioration (see below); (f) non-compliance with study protocol requirements. We will make every effort to ensure that the sessions are accessible (i.e., scheduling sessions during evening and weekend hours). We will attempt to schedule Visits 2-4 on consecutive days, but in the event that this is not possible we will allow no more than 1 week between Visits 2 & 3 and Visits 3 & 4 and no more than 3 weeks between Visits 4 & 5. Of note, if there is more than 1 week between Visit 2 & 3, we will re-do Visit 2 and proceed with the rest of the visits as normal. But once a participant completes Visit 3, Visits 4 & 5 need to be completed within the above timeframe otherwise participation will be terminated. We will make every effort to ensure that appointments are accessible (i.e., scheduling an appointment during evening and weekend hours).

Medical and Neurological Health Determination

All health information collected in the pre-screening and baseline interview (Visit 1) will be reviewed by the PI or Co-I [name], who will indicate whether the participant is medically and neurologically healthy enough to continue in the study. These determinations may be made in person, over the phone, or via e-mail, and will be documented using a Medical Review form.

Emergent Suicidal or Homicidal Risk

The clinician or research staff may remove a participant from the clinical trial if the PI thinks that the participant is at imminent suicidal or homicidal risk. The presence of suicidal ideation is evaluated at the initial assessment. Endorsement of suicidal or homicidal ideation will be addressed in session. If the patient is deemed to have specific suicidal or homicidal ideation, the PI, Co-I [name], or Co-I [name] will be immediately notified and the participant will meet with the PI and/or Co-Is [name] and/or [name], or other licensed social worker/psychologist/psychiatrist covering for the PI or Co-Is on the premises, and the police will be alerted.

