empirically derived scales that are sensitive to the effects of a variety of classes of abused drugs. The scales are the MBG (Morphine-Benzedrine Group), a general measure of drug-induced euphoria; the A (Amphetamine) scale, a measure specific for dose-related effects of d-amphetamine; the BG (Benzedrine Group), an amphetamine scale consisting mainly of items relating to intellectual efficiency and energy; the PCAG (Pentobarbital-Chlorpromazine Group), a measure of sedation; the LSD (Lysergic Acid), a measure of dysphoria and somatic symptoms; and the M scale, a measure of marijuana's effects; (4) Spielberger State-Trait Anxiety Inventory (STAI)¹³¹ (state subscale): This state subscale is used to assess the level of state (current/in the moment) anxiety in an individual; (5) At completion of drug session, participants will complete the End of Session Questionnaire (ESQ) which asks them to indicate the extent to which they think they felt a drug effect, the extent to which they think they received THC or PBO, and to rate how much they "liked its effects." They will be also asked to comment on any unusual effects they experienced, and whether they would take the substance again. In addition, physiologic measures (heart rate, blood pressure) will be collected at regular intervals throughout the drug session. (6) The Blood Draw Safety Questionnaire will be completed by the participant at the beginning of the THC/PBO session (Visit 3) and reviewed prior to blood collection at all subsequent visits.

These psychological and physiological measures are collected 1) before receiving THC or PBO on Visit 3; 2) at approximately 30 min intervals after receiving THC or PBO on Visit 3 (i.e., at 30, 60, & 90 min), immediately before going in the MRI scanner, soon after coming out of the MRI scanner; and once before the end of the visit unless otherwise specified (ESQ will be collected only at the end of the drug session; DEQ will also be collected before recall of extinction learning on Visits 4 & 5). Because the effects of the drugs may have a lingering effect, measures of the effects of the drug (DEQ) and review of adverse events will also be collected for exploratory purposes at two additional times: approximately 8 hr after drug administration.

Debriefing Session Measures

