Discovery and disclosure of incidental finding or abnormality on MRI scans: During the formal consent process, all participants will be informed about the potential risks of discovering an incidental finding or abnormality on their MRI scan. If an abnormality is found in a participant's MRI scan, the PI may ask a radiologist at the MR Facility will review the scan data and provide recommendation to the PI if the incidental finding or abnormality is something the participant should follow-up with their primary care physician about. If follow-up is recommended, the PI will contact the participant. The decision as to whether to proceed with further examination and/or treatment lies solely with the participant and his/her primary care physician.

Dronabinol

Dronabinol is associated with some adverse experiences (incidence 1%-10%) including: asthenia, increases in heart rate, palpitations, facial flush, sensory impairment, headache, nausea, vomiting, dry mouth, changes in appetite, easy laughing, euphoria, restlessness, panic attacks, anxiety/nervousness, paranoid reaction, confusion, dizziness, drowsiness, and impairment in coordination. A board-certified psychiatrist and/or physician associated with the study (Co-I [name] or Co-I [name]) or his/her physician designate, will be available during all behavioral tasks and pharmacological challenge days to evaluate and recommend further evaluation and treatment for the emergence of any adverse events/side effects.

Participants taking medications that have level 1 evidence indicating severe drug-drug interaction with dronabinol daily will be excluded. Also, we will exclude participants with a known sensitivity to the active drug or capsule excipients, including cannabinoid oil, sesame oil, gelatin, glycerin, and titanium dioxide. Pregnant participants will be excluded from participation because there is insufficient data to assure safety of the fetus during dronabinol exposure, as well as during MR scanning. In addition, nursing mothers will be excluded from the study because dronabinol is concentrated in and secreted in human breast milk and is absorbed by the nursing baby (for reference see: <http://www.fda.gov/ohrms/dockets/05n0479/05N-0479-emc0004-04.pdf>).

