The results of the breath alcohol test and urine drug and pregnancy tests performed at the beginning of Visit 3 (and Visit 1 for pregnancy test) will remain confidential. The only individuals who will have knowledge of the results of these tests are research staff directly working on the project. The breath alcohol and urine tests will be performed at the beginning of the visit. If the participant produces a positive pregnancy test at either Visit 1 or Visit 3 or reports becoming pregnant at any time during which they are active in the study, they will be withdrawn from the study at that time. At the beginning of Visit 3, if the participant (a) fails the alcohol breathalyzer test and/or (b) fails the urine drug test without any current medication use (e.g., non-illicit) which explains the positive result, the session will end at that time and the remaining visits will be rescheduled. Visits 3-5 will be rescheduled such that Visit 3 occurs within 1 week of Visit 2, otherwise the participant will need to re-do Visit 2. If the participant cannot be rescheduled or fails the urine drug test for a second time (i.e., at their rescheduled Visit 3) they will be withdrawn from the study. In the event of failed drug screen, follow-up questions will be asked to determine whether the result can be explained by a daily medication and not illicit drug use. This information will be stored in a secure computer database that uses participant codes (rather than names) as identifiers.

Other Tasks

Participants are re-assured that they can withdraw from the study at any time if they do not wish to experience the virtual snake. All participants will be informed that they are able to take a break at any time during any of the behavioral tasks.

Dronabinol

Participants are made aware of the side effects common to dronabinol in the informed consent document and again during their initial screening visit. Participants will be monitored for side effects at the pharmacological challenge visits. Participants are reassured that they can withdraw from the study at any time.

Magnetic Resonance Imaging

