Protocol deviations will be defined as noncompliance with the research protocol that does not increase risk or decrease benefit and/or affect the integrity of the data. Protocol deviations may result from the action of the participant, research staff, or MR Facility and MR staff. All protocol deviations will be documented on a participant-specific Protocol Deviation Form and will explain any deviation from the approved protocol. Protocol

deviations will be reported to the IRB and NIMH PO by the PI with the continuing review and annual progress report, respectively.

Adverse Events (AEs) are defined as any untoward or unfavorable medical occurrence in a human participant, including any abnormal sign (for example, abnormal MRI finding), symptom, or disease, temporally associated with the participant's participation in the research, whether or not considered related to the participant's participation in the research. Study personnel will ask each participant about the presence/absence of adverse events (AEs) at every study visit and document AE presence/absence. AEs will be documented in a participant-specific AE log, which will include documentation of the following information: a) grading the AE as mild, moderate, or severe; b) determining how likely the AE is related to the participant's participation in the study procedures; c) action taken regarding study participation; d) outcome of the AE; e) whether the AE was expected or unexpected (not listed as a potential side effect/risk in the protocol); and f) whether the AE is determined to be a serious adverse event (SAE).

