A serious adverse event (SAE) is any severe adverse experience occurring during the study that: (a) results in death, (b) is life-threatening (e.g., suicidality, homicidality), (c) results in hospitalization or prolongation of existing hospitalization, (d) results in persistent or significant disability, (e) is a congenital anomaly or birth defect, or (f) any other AE that, based on appropriate medical judgment, may jeopardize the subject's health and may require medical or surgical intervention to prevent one of the other outcomes listed in this definition. Moderate AEs are defined as any non-serious event which causes discomfort and requires treatment, but does not pose any significant or permanent risk of harm to the participant or require in-patient hospitalization, including social or psychological trauma causing moderate or temporary distress, significant embarrassment, stigmatization of individual or community/ group, disruption of familial/social relationships or nontrivial emotional distress. Moderate AEs will include evaluation in the emergency room not leading to hospitalization. Mild is defined as any non-serious event of less than moderate severity. All SAEs and unexpected AEs will be reported to the PI or Co-Is [name] or [name] as soon as possible within 24 hours of the study staff becoming aware of the S/AE. The PI or Co-Is [name] or [name] will determine whether participation in the study should be altered or terminated for the safety of the participant.

All unexpected problems, defined as any incident, experience, or outcome that is **unexpected, related or possibly related** to participation in the research, and suggest that the research places participants are **greater risk of harm than was previously known or recognized** will be reported by the PI to the IRB and NIMH PO as soon as possible, but within 5 business days of the PI becoming aware of the AE. For all AEs and SAEs that are deemed expected and/or unrelated to the study, a summary will be submitted by the PI to the NIMH PO with the annual progress report.

Documentation of protocol deviations will begin at Visit 1 and documentation of AEs will begin once a participant begins Visit 3 and will be collected/document until the participant completes the study procedures (at the end of Visit 5) or is withdraw from the study (by self or my research staff).

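### AE documentation stops at withdrawal even after dosing, so late or unresolved events in participants who leave are not actively captured, and no section follows a post-dose pregnancy to its outcome

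*Combined protocol and SAP*

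**What the plan says.** Section 5 (Data and Safety Monitoring Plan) fixes both ends of the AE record. At the start, "documentation of AEs will begin once a participant begins Visit 3", which is the dosing visit. At the end, AEs "will be collected/document until the participant completes the study procedures (at the end of Visit 5) or is withdraw from the study", whether the participant or the staff decide on withdrawal. Within that period staff are to "ask each participant about the presence/absence of adverse events (AEs) at every study visit and document AE presence/absence". The participant's log must give the severity, the relation to study procedures, any action on participation and how the event ended. One more contact is planned under THC/PBO Day Measures, where a "review of adverse events will also be collected for exploratory purposes at two additional times: approximately 8 hr after drug administration". That sentence promises two times and names one.

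Several rules turn events after dosing into withdrawal:
- Termination Criteria, on visit windows: "Visits 4 & 5 need to be completed within the above timeframe otherwise participation will be terminated".
- Termination Criteria also list deterioration, new illness and risk of harm as possible grounds, and Section 5 lets the investigators end participation because of an AE.
- The section on confidentiality of breathalyzer, drug and pregnancy tests covers a participant who "reports becoming pregnant at any time during which they are active in the study, they will be withdrawn from the study at that time".

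On pregnancy, the SAE definition includes an event that "is a congenital anomaly or birth defect", and the Dronabinol risk section excludes pregnant women because "there is insufficient data to assure safety of the fetus during dronabinol exposure".

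**The concern.** Withdrawal closes the AE record at a moment that may itself depend on treatment. If THC makes some people leave, the THC arms lose more AE observation time than placebo. Two planned uses of the data would feel this: the formal comparison of AE frequencies, and the second interim criterion, which allows no THC-related event above mild severity beyond what is seen on placebo. The interim look can lead to a dosing amendment.

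The plan also conflicts with itself. It requires an outcome for every logged AE, but gives no way to obtain one when the event is still open at withdrawal. And it names birth defects as serious events without any procedure by which one would come to light.

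**Working it through.** **1. The plan's own figure.** Inputs: 26 per PTSD condition and 25% not completing (C.2 Overall Study Design; Nature of Participant Population). 26 × (1 − 0.25) = 19.5, which the plan gives as about 20. It reproduces.

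**2. How many dosed participants could be affected.**
- THC: 2 × 26 = 52, and 52 × 0.25 = 13. Placebo: 26 × 0.25 = 6.5.
- These are upper bounds at the planned sample size. Randomisation is at Visit 2 and the capsule is given at Visit 3, so the 25% includes people lost before dosing, such as those who fail the urine drug test twice. The documents do not split the two.
- Assume that 25%, 50% or 100% of non-completers leave after dosing. On THC this gives 13 × 0.25 = 3.25, 13 × 0.50 = 6.5, or 13: about 3 to 13 of 52.

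**3. Length of the AE window after dosing.**
- Termination Criteria: at most 1 week to Visit 4 and 3 more to Visit 5, so 7 + 21 = 28 days.
- The visit list under Involvement of Human Participants counts the 3-week limit for Visit 5 from extinction, which gives 21 days. The two limits need reconciling.
- On the intended schedule the window is only about 7 or 8 days.

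**4. What contact remains, by route of departure.**
- Leaves during Visit 3: AEs up to departure are logged. Whether the review at about 8 hours still takes place is unclear. It is timed from dosing and is not expressly cancelled, but Section 5 has already closed documentation.
- Misses the Visit 4 window: Visit 3 and the 8-hour review, then nothing.
- Misses the Visit 5 window: the same plus Visit 4, then nothing.
- Terminated for an AE, or withdrawn for pregnancy: the event and the action taken are logged, but there is no later contact to establish the outcome.

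The only telephone follow-up after a session (Magnetic Resonance Imaging, under Protection Against Risk) concerns anxiety in the scanner, is made if the team has doubts, and is not tied to the AE log.

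**5. Pregnancy.** Taking 266 days from conception to birth (an assumption), the AE window covers 21/266 = 7.9% to 28/266 = 10.5% of that time. A completer who conceived near dosing would therefore have no birth outcome recorded either. The withdrawal rule shortens the window further but is not the sole cause.

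**6. The interim look.** It is triggered when about 10% of the THC group has completed: 52 × 0.10 = 5.2, so about 5 people. The text does not say whether dosed participants who withdrew are counted. With so few, one wrongly graded event could matter. As an illustration, Section 5 treats an emergency-room evaluation without admission as a moderate AE. If someone leaves Visit 3 with an event graded mild and is seen in an emergency room that night, the log still says mild unless someone happens to hear of it.

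**The case against.** A reader might infer that dosed participants who leave disappear from the safety data. The documents do not support that. Documentation starts at the dosing visit, the log records action on participation, events also enter a study-wide log, and no section removes withdrawn participants from the AE analyses. An event above mild severity that drives someone out is recorded and counts against the interim criterion.

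The acute period is also largely covered. Dosing is a single oral capsule, peak levels are expected at about 120 minutes, and Visit 3 lasts about 5 hours with repeated measures. The interim criterion concerns acute administration, so what is lost is delayed onset, later worsening and late resolution. The documents give no rate for any of these.

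Three further points carry weight:
- The termination criteria are mostly permissive, so deterioration need not close the record.
- The Suicide Risk section promises follow-up in all cases. It is tied to the C-SSRS, however, which Table 1 schedules only at screening, so its reach after dosing is limited.
- Reporting clocks run from when staff become aware of an event, so something learned by chance could still be reported. It is therefore too strong to say that a birth defect could never be observed. Pregnancy is also an exclusion, with urine tests at Visit 1 and before dosing, so few cases would be expected.

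All of this limits the size of the problem. None of it supplies active follow-up after withdrawal or a route to the outcome of an open event.

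**Conclusion.** The point holds as an ascertainment gap. After a dosed participant leaves, AEs that start, worsen or remain open are not actively sought, and the required outcome field has no source for events still open. Post-dose pregnancies have no outcome follow-up, for completers as well as for those withdrawn.

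At most about 13 of 52 THC participants are affected, and about 3 to 13 under the assumed split. This rests on the plan's 25% and its planned 78 PTSD participants. The plan also allows up to 175 to be enrolled in total, and the count would need redoing if that allowance were used.

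It is tempting to conclude that the AE comparisons are biased in favour of THC. That would need departures to be caused by THC and later events to be missed, and the documents give neither rate. Unequal observation time between arms is possible; its direction is conditional and its size cannot be computed. The Aim 1 analyses of brain activation and extinction recall are not affected. This is a change that should be made because it is cheap and improves safety data, not one on which the trial's validity depends.

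**What to change.** Amend Section 5 for anyone who has taken a capsule and has not withdrawn consent to contact:
- Continue AE collection by telephone to the planned Visit 5 date, regardless of withdrawal or termination.
- Follow events still open at that date until resolved or stable.
- State that the review at about 8 hours also applies to those who leave on the dosing day, and reconcile that sentence's two promised times with the one it names.
- Follow any pregnancy reported after dosing to its outcome.
- State that AE comparisons, including the interim look, use all dosed participants.

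The cost is protocol wording, consent wording if it does not already allow such contact, and a few calls for at most about 20 people (78 × 0.25 = 19.5), with a little extra tracking of those who have left. No dose, visit or treatment rule changes.

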C.2. Overall Study Design: The R61 study will employ a randomized, double-blind, PBO-controlled, between-subjects design, coupling a standard Pavlovian fear conditioning paradigm during fMRI with an acute pharmacological challenge using oral dronabinol (THC) or PBO *prior to fear extinction* in PTSD patients and test recall of extinction learning 24 hr (proximal memory) and 1 week later (distal memory) when spontaneous recovery is expected to be robust. 78 PTSD participants will be randomized to 1 of 3 conditions: single doses of 5mg or 10mg of THC, or PBO, using covariate adaptive randomization¹¹⁸⁻¹²², in which a new participant is sequentially allocated to a treatment condition by taking into account baseline characteristics (e.g., CAPS-5, age, sex, race) and previous assignments of participants¹²³, with 26 PTSD participants per condition. However, because randomization does not guarantee comparability across groups, the groups will be compared to ensure reasonable similarity in the distributions of their baseline characteristics. The imbalance in covariate levels will be measured by a χ^2 goodness-of-fit test (for categorical covariates) or t-test (for quantitative covariates). Variables with significant group differences ($p<0.05$) will be included as covariates in primary analyses. Additionally, 26 healthy trauma-exposed controls (TEC; demographically matched) will be included and tested at comparable time points to separate the impact of trauma from the impact of PTSD. The TEC group will not receive THC, any drug-related monitoring, or undergo blood draws but will otherwise complete all phases of the

experiment. With the conservative anticipation that about 25% will fail to complete all parts of the study, we estimate about 20 PTSD subjects in each condition (60 PTSD participants in total) and 20 TEC participants in total. Participants will be recruited from the Detroit community and mental health clinics (**see 'Protection of Human Participants'**).

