Visit 2: Fear Acquisition: Approximately 1 hr for all participants. Participants are considered enrolled in the study once they have begun Visit 2 (if enrolled in PTSD group, participant will be randomized). Visit 2 will occur within 6 months of Visit 1. If more than 6 months have passed, we will re-do Visit 1 before the participant is able to complete visits 2 – 5.

Visit 3: Fear Extinction: Approximately 5 hr for those receiving a capsule (PTSD groups) or approximately 3 hours for those not receiving a capsule (TEC group)

Visit 4: Fear Extinction Recall and Fear Renewal Test (approximately 24 hr after extinction, but no more than 1 week later): Approximately 1.5 hr

Visit 5: Fear Extinction Recall, Fear Renewal Test, & Debriefing (approximately 1 week after extinction, but no more than 3 weeks later): Approximately 1.5 hr

Nature of Participant Population: Participants of both genders will be included in the study and the age range of participants will be from 18-60. Persons below 18 or above 60 are excluded because beyond this range age may influence response to the drugs. Furthermore, the relatively small age range is intended to reduce variation in performance on the behavioral task. There are no enrollment restrictions based upon race or ethnic origin. Candidates will undergo a structured clinical psychiatric interview¹⁵⁰ and complete questionnaires related to their general physical health, current medications, with a detailed section on current and lifetime drug and alcohol use. This study will not involve vulnerable populations.

The number of participants expected to participate is 104: 78 trauma-exposed participants with PTSD and 26 trauma-exposed participants without PTSD (TEC; demographically matched). There will be 3 experimental groups: PTSD participants will be assigned to 5mg of THC (n=26), 10mg of THC (n=26), or a placebo (PBO) (n=26). The 26 TEC participants will not receive THC or PBO. With the conservative anticipation 25% will fail to complete all parts of the study, we estimate 20 PTSD participants in each condition (60 PTSD participants in total) and 20 TEC participants will complete the study for a total of 80 participants. Participants will be recruited from the Detroit community and mental health clinics. We will enroll up to 175 participants to guarantee enough viable data and to account for participant drop out.

Recruitment

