Vulnerable Populations

This study will include women of child-bearing potential and college students. However, we will conduct urine pregnancy tests at the screening visit (Visit 1) and at the beginning of Visit 3 to make sure that women are not pregnant. Of note, if the participant is unable to provide a urine sample at Visit 1 (e.g., currently menstruating), we will conduct a urine pregnancy test at the beginning of visit 2. We will also conduct pregnancy tests if the study staff and/or participant have reason to believe they may be pregnant. In addition, participation of college students in this study is completely voluntary, as it is for all participants, and will not be required by any course.

Study Group Assignment

Individuals with PTSD will be randomized to a THC or PBO condition. In our previous studies we have shown that 7.5mg of THC facilitates extinction recall and modulates prefrontal and hippocampal activation in healthy humans volunteers^{55,113}. Moreover, PI [name] has preliminary data to suggest that 7.5mg of THC may facilitate extinction recall in PTSD, but it is not known whether this is the MED. This is an initial step in translation to be tested in the R61 phase. Therefore, we will have a low 5mg condition and a high 10mg condition should 5mg be too low to detect effects. Of note, a 10mg dose of THC does not typically produce anxiety¹⁵¹ or strong negative effects on cognition¹⁵². We aim to identify the MED that facilitates recall of extinction learning. Dronabinol is administered only by the oral route and will be placed in opaque capsules with dextrose filler. Placebo capsules will be identical in appearance but will contain only dextrose. All capsules will be administered to participants in double-blind conditions and participants assigned to receive dronabinol (two-thirds of the PTSD participants) will only receive dronabinol on one occasion.

Study medication, dronabinol or PBO, will be dispensed to participants by PI [name], who possesses a Schedule II-V controlled substance research license through the State of Michigan and the DEA and has experience in the use of dronabinol and PBO in human participant research. A registered pharmacist will handle

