Weekly meetings of the research staff of this study will be conducted that will include review of accrual, consenting procedures, protocol adherence, AEs, and quality control of all data obtained from the study in the previous weeks. Minutes of these meetings will be recorded, signed by the PI, and archived in a Regulatory Folder on the lab server. In addition, to participant-specific protocol deviation forms, protocol deviation will also be documented in a study-wide deviations log to facilitate monitoring and reporting to regulatory authorities. Similarly, AEs will be also documented in a study-wide AE log, which will be used to facilitate safety monitoring and identify AE trends across subjects, as well as overall AE reporting to the IRB and NIMH.

We will conduct a preliminary analysis during the early stages of data collection (once \approx 10% of the THC group has completed the study) to assess the efficacy and safety of the 5mg and 10mg doses and submit an amendment to adjust the dosing as needed (e.g. if 10mg shows significant improvement over 5mg, a further

increase in dosing [15mg] would be worthwhile). Our efficacy and safety metrics are based on the following criteria:

- 1) a. At least a medium effect size (Cohen's $d \geq 0.05$) between THC and PBO conditions in BOLD responses in *a priori* ROIs (vmPFC and/or HPC) and/or peripheral measures (SCR, US expectancy, SUDS) during recall of extinction learning; or
 - b. Relationship between change in BOLD responses in *a priori* ROIs (vmPFC and/or HPC) and/or change in peripheral measures (SCR, US expectancy, SUDS) during recall of extinction learning in THC (vs. PBO) is of at least a medium effect size ($r \geq 0.30$).
- 2) There will be no adverse events of more than mild severity that are rated as possibly, probably, or definitely related to acute administration of THC (more than PBO) in PTSD participants.

We will apply O'Brien-Fleming¹⁷⁹ type monitoring bounds as guidelines for the decisions regarding continuation or early termination of the trial. In addition to efficacy comparisons, frequency of AEs along with formal statistical comparisons of the frequency of AEs will be performed.

Reporting responsibility

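### The look at about 10% of the THC group judges efficacy and may lead to a dosing amendment on about 5 THC participants, too few to tell an effect from noise, and no stated rule links the criteria to a dosing action

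*Combined protocol and SAP*

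**What the plan says.** Section 5 plans a preliminary analysis early in data collection, when about "10% of the THC group has completed the study". Its purpose is "to assess the efficacy and safety of the 5mg and 10mg doses and submit an amendment to adjust the dosing as needed". The illustration is that "if 10mg shows significant improvement over 5mg, a further" increase would be worthwhile.

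The section then lists the metrics:

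- **Criterion 1a:** "At least a medium effect size (Cohen's $d \geq 0.05$) between THC and PBO conditions", on vmPFC and/or HPC activation and/or SCR, US expectancy or SUDS during extinction recall.
- **Criterion 1b**, an alternative to 1a: a correlation of at least 0.30 between changes in these measures.
- **Criterion 2:** no more-than-mild adverse events related to THC beyond placebo.

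It adds "We will apply O'Brien-Fleming" type bounds as guidelines for continuing or terminating the trial.

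The allocation under Nature of Participant Population is "5mg of THC (n=26), 10mg of THC (n=26), or a placebo (PBO) (n=26"). Study Group Assignment gives the purpose: "We aim to identify the MED that facilitates recall of extinction learning".

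**The concern.** A decision about the doses under test may be taken after 2-3 completers per dose. The efficacy criterion is an any-of-several rule on effect sizes, with no significance requirement, so noise alone can satisfy it. The example trigger has the opposite problem: it asks for statistical significance between two groups of 2-3.

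Aim 1 rests on concurrent randomised 5mg, 10mg and placebo arms. If the doses changed on the strength of this look, that comparison could be lost or thinned. The plan does not say how participants treated before and after a change would be analysed, or how many each arm would then contain.

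**Working it through.** **The plan's own figures.** The documents give no operating characteristics for this look. The nearest figure is in the R61 Power Analysis: more than 80% power for d = 0.72 with 20 completers per group after multiplicity adjustment. An unadjusted two-sided 0.05 t-test of 20 v 20 at d = 0.72 gives 60%. That gap is a separate matter; 60% serves below only as a reference.

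**Size of the look.** C.2 has PTSD participants randomised "with 26 PTSD participants per condition". The THC group is 2 x 26 = 52, and 0.10 x 52 = 5.2, or 2-3 per dose. Counting from 40 expected THC completers gives 4. Placebo completers are not stated; 2-3 is my assumption from 1:1:1 allocation.

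**Criterion 1a with no THC effect.** The printed threshold is 0.05, but it is labelled medium. I use 0.50 as an assumption, which favours the plan because it is harder to pass. For THC 5 v placebo 3:

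- The standard error of the observed d is about sqrt(1/5 + 1/3) = 0.73.
- One measure: P(t with 6 df >= 0.50/0.73 = 0.68) = 26%.
- Any of five measures, by simulation with normal outcomes:

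| Assumed correlation between measures | Chance of meeting 1a at d >= 0.50 |
|---|---|
| 0 | 78% |
| 0.3 | 66% |
| 0.6 | 54% |
| 0.9 | 39% |

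The independent case checks by hand: 1 - 0.74^5 = 78%. At the printed 0.05, one measure passes 47% of the time, and any of five passes 62-96% over the same correlations.

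**Criterion 1b with no true correlation.** For r >= 0.30 in the predicted direction, t = 0.30 x sqrt((n - 2)/(1 - 0.09)). With n = 5, t = 0.54 on 3 df, giving 31%. With n = 8, t = 0.77 on 6 df, giving 24%. This is for one pair of measures; the text allows several.

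**The 10mg v 5mg example at 3 v 2.** C.2.5 sets two-tailed 0.05.

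- Smallest significant d: 3.182 x sqrt(1/3 + 1/2) = 2.91.
- Power (noncentral t): 9% at d = 0.72, and 21% at d = 1.5, the top of the range in the R61 Power Analysis.
- False finding that 10mg is better: 0.05/2 = 2.5% on one measure. If any of five unadjusted measures counts, it is 6-12% for correlations 0.9 to 0.
- If any of five unadjusted measures counts and d = 0.72 on each, the example fires 25-42% of the time over 2 v 2 to 3 v 3 and correlations 0 to 0.5. With the Hochberg adjustment named in C.2.5 it fires about 7-12% of the time.

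**What a change could cost**, in unadjusted power at d = 0.72 against the 60% reference:

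- 10mg arm stopped at 2-3 participants and compared with 20 on placebo: 15-20%.
- A fourth arm fitted within the 78, at about 14-15 completers per arm: 45-48% per pair.
- A replacement arm of 23 enrolled (23 x 0.75 = about 17 completers) v 20: 56%.

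**The case against.** The strongest reply is that section 5 does not make criterion 1a or 1b a trigger for changing the dose. They are called metrics and compare THC with placebo; a chance pass could equally support carrying on with both doses. A reader might infer from the 39-78% range that the plan produces a wrong dose decision in most runs when THC does nothing. The documents do not support that: the only stated dose-change example is a different comparison, which fires falsely in about 2.5% of runs on one measure and 6-12% on any of five. This part of the reply stands.

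Three other strong readings also go too far.

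- **That the three-arm comparison would be destroyed.** Any change needs an amendment, the wording is conditional, and the safety criterion also applies. Only 2-3 participants per arm would precede a change. The enrolment ceiling of 175, against 104 planned, leaves room to refill arms, and 5mg v placebo could survive intact.
- **That the O'Brien-Fleming bounds fail to control the dosing decision.** They are tied to continuation or termination. At 10% information a bound of that shape is about 1.96/sqrt(0.10) = 6.2, and severity that early is what the method intends. The plan names neither a number of looks nor a spending function.
- **That an upward example contradicts the aim of finding the MED.** Study Group Assignment includes 10mg in case 5mg is too low to detect effects, so an upward step is compatible with that aim. The link still needs to be written down.

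None of this supplies a reason to judge efficacy on about 5 treated participants. That the criteria are not linked to an action is itself a gap.

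**Conclusion.** The concern holds in this form: the efficacy metrics at the 10% look carry almost no information, and the plan does not connect its THC-versus-placebo criteria to its 10mg-versus-5mg example. With no effect, criterion 1a read as d >= 0.50 is met by chance 26% of the time on one measure. On any of five it is met 54-78% of the time for correlations from 0.6 down to 0, and 39% at 0.9. Criterion 1b adds a further chance route of 24-31% per pair. The significance example rarely fires on a single or Hochberg-adjusted comparison, even when the planning effect is real.

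These figures assume normal outcomes, 3 placebo completers for criterion 1a, a 3 v 2 split between doses for the example, and the stated correlations; none of these is in the documents. At correlation 0.9, criterion 1a alone passes less than half the time, so a claim that it usually passes by chance depends on the correlation. Loss of the planned dose comparison is a possible consequence, not a certain one.

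**What to change.** In section 5, use the 10% look for safety only (criterion 2 and adverse event frequencies), and state that no efficacy conclusion will be drawn from criteria 1a or 1b at that size. If an efficacy look is wanted, pre-specify it for a later point with adequate data in all three PTSD arms. Give its measures, its multiplicity handling and which result bears on which decision. State that if the arms change, participants are compared only with concurrently randomised placebo.

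The sponsor must also reconcile three pieces of text: the THC-versus-placebo criteria, the 10mg-versus-5mg example, and the MED aim in Study Group Assignment. No dose or dosing rule is proposed here.

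The change is protocol wording. It gives up an early efficacy read that is close to noise and keeps the early safety review.
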